1.4 Study Rationale and Risk Analysis (Risks to Benefits Ratio)

1.4.1 Study Rationale

The SimPull is a standalone lateral patient transfer device that can be used in environments with limited ceiling access and confined spaces in the acute care setting. The current available products to support lateral transfers, all have the same problem; they require a separate product for the patient to be on top of during transfer. To get patients on these transferrable surfaces is an entirely manual process referred to commonly as “log-rolling” must be performed. This manipulation is attributable to up to 50% of injuries related to lateral transfer. Even with these products available, nurses sustain more injuries than any other profession in any other industry and patient transfer, specifically lateral transfer is a major contributor. When nurses sustain these injuries, it makes them vulnerable to further injury, sometimes unable to participate in transfers post-injury. This creates additional burden and increased risk to uninjured staff as they’re held accountable to do the same transfers without support from injured staff.

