2.2 Secondary Objective

The secondary objective of this study is to validate the SimPull increases staff satisfaction of lateral patient transfer.

3 Study Design

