3.2 Primary Study Endpoints

Endpoint 1: Difference between transfer methods in time for transfer.

Endpoint 2: Difference between transfer methods in number of staff involved in transfer.

Endpoint 3: Difference between transfer methods in proportion of transfers following the OSHA mandate of no more than 35 lbs. lifted per staff member (lbs. lifter per staff member calculated as: weight of patient in lbs. divided by number of staff involved in transfer).

Endpoint 4: Paired difference in satisfaction scores (satisfaction with current transfer method and with SimPull) on staff questionnaires.

Endpoint 5: Paired difference in self-rated risk of injury (with current transfer method and with SimPull) on staff questionnaires.

4 Subject Selection, Enrollment and Withdrawal

Patient selection will be based on set inclusion and exclusion criteria of patients scheduled for procedures in the cardiac catheterization and electrophysiology procedural area. If the patient meets eligibility requirements, consent will be obtained using a written consent process. **The Principal Investigator and Co-Principal Investigator or study members** with recorded conflict of interest do not have consenting privileges and will not participate in the recruitment or consenting process. Using REDCap, the study team will enter data based off transfer observations. If patient consents and no IRB approved study member is available to perform the transfer, the patient will be excluded from the study. If the patient meets inclusion criteria, the clinical research coordinator will validate that a study member is present to transfer the patient prior to consent,. Enrollment will begin with the first 50 patients using the current method of transfer-followed by the pre-survey of staff. Staff will then receive training on the SimPull transfer device and the next enrolled 50 patients will be transferred with SimPull; followed by post-survey of staff. Study members are defined as employees (registered nurses and technicians) of Mayo Clinic assigned to the cardiac catheterization and electrophysiology procedural areas.

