6.2 Statistical Methods

Descriptive Statistics

Patient and transfer characteristics will be descriptively summarized by transfer type. Staff questionnaires will be descriptively summarized. The difference between transfer methods in time for transfer and number of staff involved in transfer will be tested using two-sample t-tests. A possible secondary analysis would test differences using a regression model adjusting for differences in patient or transfer characteristics. The difference between transfer methods in proportion of transfers following the OSHA mandate of no more than 35 lbs. lifted per staff member will be tested using a Chi-square or Fisher's exact test. A possible secondary analysis would test differences using a regression model adjusting for differences in patient characteristics. The paired differences in mean staff satisfaction scores and self-rated risk of injury scores will be tested using paired tests.

Primary Hypothesis:

SimPull lateral transfer device is a more efficient and safe method of lateral patient transfer than current methods of lateral transfer.

By recording patient weight and the number of clinicians engaged during manual transfers we can calculate the force needed by each individual. Example: Patient weight: 265 lbs., five clinicians: 53 lbs. per clinician (51% higher than the 35 lb. OSHA mandate). This data collection allows risk assessment of clinician injury during transfer in each location by

establishing weight pulled by clinicians and the number of transfers per day. Using this we can also forecast force required and risk of injury over time. Time to complete in seconds will be recorded for each lateral transfer.

Secondary Hypothesis:

Use of the SimPull device for lateral transfers will increase staff satisfaction and be a preferred method of lateral patient transfer.

Data collected pre and post SimPull implementation

- Employee Satisfaction
- Employee Perception of Injury Risk

Staff/Clinician Participant Survey:

Part 1 of Survey – Pre-Training

1. What is your preferred method for performing lateral patient transfers?
 - a. Manual, Assisted, Ceiling Lift, or Air Mattress
2. Do you feel at risk of injury performing lateral patient transfers?
 - a. No Risk, Minimal Risk, Neutral, Some Risk, High Risk
3. How likely do you feel you are to be injured during lateral patient transfer?
 - a. Not at all likely, Not Likely, Neutral, Likely, Very Likely

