4. What type of injury do you think you would have during lateral transfers?
 - a. Open response
5. What preventative measures do you take to avoid injury during lateral transfers?
 - a. Open response
6. Are you satisfied with current lateral patient transfer methods?
 - a. Yes/No

Part 2 of Survey – Post Training

1. What is your preferred method for performing lateral patient transfers?
 - a. Manual, Assisted, Lift, or SimPull
2. Do you feel at risk of injury performing lateral patient transfers using the SimPull?
 - a. No Risk, Minimal Risk, Neutral, Some Risk, High Risk
3. How likely do you feel you are to be injured during lateral patient transfer using SimPull?
 - a. Not at all likely, Not Likely, Neutral, Likely, Very Likely
4. What type of injury do you think you would have during lateral transfer using SimPull?
 - a. Open response
5. What preventative measures do you take to avoid injury during lateral transfers using SimPull?
 - a. Open response
6. Are you satisfied with lateral patient transfer using SimPull?
 - a. Yes/No

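### Survey item 1 drops Air Mattress when SimPull is added; with other preferences stable, that removal can only leave the descriptive SimPull share unchanged or raise it (minor)

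*Combined protocol and SAP*

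**What the plan says.** Section 6.2 prints a two-part staff questionnaire. Item 1 has the same stem in both parts: "What is your preferred method for performing lateral patient transfers". In Part 1 (pre-training) the options are "Manual, Assisted, Ceiling Lift, or Air Mattress". In Part 2 (post training) they are "Manual, Assisted, Lift, or SimPull". SimPull enters, Air Mattress leaves, and Ceiling Lift becomes Lift. Neither list has an Other option, and no reason for the change is given.

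The item bears on one clause of the secondary hypothesis in section 6.2: "Use of the SimPull device for lateral transfers will increase staff satisfaction and be a preferred method of lateral patient transfer". No test is named for it, so it falls under the general statement "Staff questionnaires will be descriptively summarized". The paired tests in section 6.2 are for satisfaction and self-rated injury risk. Section 2.2 sets the secondary objective as staff satisfaction only, and preference is not among the five endpoints in section 3.2.

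**The concern.** Item 1 is the only question about preferred method, so the Part 2 SimPull percentage is the natural evidence for the preference clause. Items 2 to 6 of Part 2 ask about SimPull or its use. Item 1 instead keeps the general stem and lists three other methods, so it is a comparison among methods. One alternative that staff could name before training can no longer be named once the study device is on the list. A member of staff who still prefers it must choose something else or leave the item blank, and some of those answers may go to SimPull. At stake is how a descriptive percentage is read, not any tested result.

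**Working it through.** The documents state no preference figure, so there is none to reproduce. The check compares the two lists and then bounds the effect of removing Air Mattress.

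**Lists side by side (section 6.2, item 1)**

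| Option | Part 1 | Part 2 |
|---|---|---|
| Manual | yes | yes |
| Assisted (undefined) | yes | yes |
| Ceiling Lift / Lift | Ceiling Lift | Lift |
| Air Mattress | yes | no |
| SimPull | no | yes |
| Other | no | no |

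**Bound.** Suppose Part 2 had offered the Part 1 options plus SimPull. Let
- s = share who would choose SimPull,
- a = share who would choose Air Mattress, with s + a ≤ 1,
- r = fraction of the air-mattress staff who pick SimPull when their option is missing,
- k = fraction of them who skip the item, with r + k ≤ 1.

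Assume that everyone else answers as they would on the full list. Among those who answer item 1:

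- Observed SimPull share = (s + a·r) / (1 − a·k).
- Rise = (s + a·r) / (1 − a·k) − s = a·(r + s·k) / (1 − a·k).

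Every term is non-negative, so the rise is at least 0. It is at most a when r + s·k ≤ 1 − a·k, that is, when r + k·(s + a) ≤ 1. This always holds, because s + a ≤ 1 and r + k ≤ 1. A grid of 1,756,950 combinations of s, a, r and k gave no value outside 0 to a.

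If blanks are kept in the denominator, the share is s + a·r and the rise is a·r. That also lies between 0 and a, but skipping then adds nothing.

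**Illustration.** The documents give no preference rates, so s = 40% and the values of a are assumptions. Shares are among those who answer.

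| a | All pick another non-SimPull option (s) | All skip: s/(1 − a) | All pick SimPull: s + a |
|---|---|---|---|
| 0% | 40% | 0.40/1.00 = 40.0% | 40% |
| 10% | 40% | 0.40/0.90 = 44.4% | 50% |
| 20% | 40% | 0.40/0.80 = 50.0% | 60% |
| 30% | 40% | 0.40/0.70 = 57.1% | 70% |

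**What is not touched.** Section 6.1 powers transfer time and number of staff only. Endpoints 1 to 3 come from transfer records. Endpoints 4 and 5 concern satisfaction and self-rated injury risk. None uses item 1.

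**The case against.** The strongest case against is that little depends on the item. Preference is not an endpoint and has no test. Section 6.2 lists satisfaction and perceived injury risk as the data collected before and after, not preference. The hypothesis speaks of a preferred method without a threshold. The two lists could never be identical, because SimPull belongs only in Part 2. The effect may also be zero: perhaps no staff prefer air mattresses, or those who do may tick Assisted. All of this stands, and it makes the point minor. It does not remove the point, because a zero effect cannot be assumed either and the omission serves no stated purpose.

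Three stronger readings are tempting, and the documents do not support them.

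- A reader might infer that the whole revised list can only favour SimPull. The bound covers the removal of Air Mattress alone. Lift is a broader label than Ceiling Lift, so staff with another kind of lift in mind might now choose it instead of SimPull.
- A reader might try to bracket the true share from linked answers. Endpoint 4 is a paired measure ("Paired difference in satisfaction scores (satisfaction with current transfer method and with SimPull) on staff questionnaires"), which suggests that answers will be linked. With n linked staff, S choosing SimPull in Part 2 and X of those S having chosen Air Mattress in Part 1, the bracket would run from (S − X)/n to S/n. It is valid only if everyone who prefers an air mattress after training also chose it before. Take n = 2. One person moves from Manual to preferring Air Mattress and, lacking that option, ticks SimPull. The other moves from Air Mattress to Manual. Then S = 1 and X = 0, the bracket is 1/2 to 1/2, and the true share is 0. The lower figure also counts genuine moves from Air Mattress to SimPull against SimPull.
- A reader might infer that a competitor was removed on purpose, since section 1.4.1 says of current products that "they require a separate product for the patient to be on top of during transfer". That passage concerns all available products and does not single out air mattresses. The documents do not say which products these labs use.

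The number of respondents is also unclear. Section 3.1 speaks of a survey for the 100 transfers, while section 4 describes one pre-survey and one post-survey of staff. The bound is in shares and does not depend on this.

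**Conclusion.** The point holds as a minor correction. The option lists differ under an identical stem, and Air Mattress is missing from the only list that contains SimPull. Removing it can raise the SimPull share among those who answer by anything from 0 up to the share who would have chosen Air Mattress. That share is not in the documents and may be zero. The direction rests on one assumption: staff who would not have chosen Air Mattress answer as they would on the full list. No direction is claimed for the change from Ceiling Lift to Lift; it only makes the two lists harder to compare. The consequence is confined to the descriptive support for the preference clause of the secondary hypothesis.

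**What to change.** Before the post-survey opens, change the Part 2 item 1 options to Manual, Assisted, Ceiling Lift, Air Mattress and SimPull. Leave Part 1 as it is. Section 4 places the post-survey after the SimPull transfers, so the edit is possible even if the pre-survey is complete. The cost is one item edit with routine IRB sign-off; no extra staff or patients are needed.

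If the post-survey is already done, report the SimPull share with a plain statement that Air Mattress was not offered, and put the Part 1 Air Mattress share beside it. That share gives a sense of scale and is not a correction. Do not present (S − X)/n to S/n as an interval that contains the true share. The cost is one sentence and one percentage from data already collected.

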6.3 Subject Population(s) for Analysis

All-treated population that was transferred using the SimPull device in the cardiac catheterization and electrophysiology procedure area.

7 Safety and Adverse Events

All adverse events occurring during the study, including those not meeting the criteria of an Unanticipated Adverse Device Effect (UADE) will be recorded on the appropriate case report form. Records of these events will be maintained and reports submitted to the FDA and IRB according to the regulatory requirements. Expected clinical adverse events and nonsignificant (not serious) clinical adverse events will not be reported. Expected clinical adverse events and anticipated adverse device effects are those listed in Section 1.5.2.

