1.4.2 Anticipated Risks

SimPull is a standalone lateral patient transfer device, that is not yet approved for market, making it an investigational use device. SimPull is meant to be used in many environments, meaning that in interacting with products that are not specifically made to be compatible with SimPull could result in some risk. Specifically, SimPull attaches to sheets under patients, if the sheets are not positioned well, the patient could turn during transfer. SimPull engages to the surfaces that the patient is being transferred to and from, if any surface is not in the braked or locked position there may be risk to the transfer. These risks are mitigated through sensors that prevent transfer if positioning is jeopardized. The last risk is that the device pulls the patient across one surface to another, in doing so there is some friction, though it has been intentionally reduced as much as possible, this friction could result in risk to the patient.

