4.4 Early Withdrawal of Subjects

4.4.1 When and How to Withdraw Subjects

Subjects may choose to withdraw from the study (withdrawal of consent) at any time prior to use of the SimPull for lateral transfer. Any subject that withdraws their consent will be replaced so data is collected on 50 total subjects per transfer method.

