5.2 Method for Assigning Subjects to Treatment Groups

Patient selection will be based on set inclusion and exclusion criteria of patients scheduled for procedure in the cardiac catheterization and electrophysiology procedural area. If the patient meets eligibility requirements, consent will be obtained using a paper consent process.

Patients will not be randomly assigned to treatment group. The first 50 patients (or greater than 50 if there are withdrawals) will have the current method of transfer. The next 50 patients (or greater than 50 if there are withdrawals) will have the SimPull device for transfer.

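### Section 6.3 admits patients by actual transfer with SimPull rather than by assigned phase and has no rule for blocked or converted attempts; excluding these would overstate SimPull's time and staff savings

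*Combined protocol and SAP*

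**What the plan says.** - **Analysis set (section 6.3).** The only population defined is "All-treated population that was transferred using the SimPull device in the cardiac catheterization and electrophysiology procedure area".
- **Assignment (section 5.2).** Patients are not randomised. The first 50 have the current method, and then: "The next 50 patients (or greater than 50 if there are withdrawals) will have the SimPull device for transfer".
- **Foreseen failure (section 1.4.2).** After describing poorly placed sheets and unlocked surfaces, the protocol says: "These risks are mitigated through sensors that prevent transfer if positioning is jeopardized". Section 1.3 reports no clinical data on the device, so the frequency of such blocks is unknown.
- **Endpoints (section 3.2).** Endpoint 1 is "Difference between transfer methods in time for transfer" and Endpoint 2 is "Difference between transfer methods in number of staff involved in transfer". None of the five endpoints counts completed, failed or converted SimPull transfers, although feasibility is the first objective listed in section 2.
- **Timing (section 6.2).** "Time to complete in seconds will be recorded for each lateral transfer". Start and stop points are not defined for an attempt that fails.

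The protocol does not say how to classify, time, staff-count or report a SimPull attempt that is blocked, abandoned or completed by another method.

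**The concern.** Entry to the SimPull set depends on an event after assignment. Take a patient enrolled in the SimPull phase whose attempt is stopped by the sensors and who is then moved by hand. In ordinary language that patient was not moved with SimPull, so section 6.3 as worded leaves the patient out.

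The current-method phase has no matching loss, because a difficult manual transfer is still a manual transfer. If conversions take longer and need more people than a smooth SimPull transfer, dropping them shortens the SimPull mean time and lowers its mean staff count. Both endpoints serve the primary efficiency objective in section 2.1. The same omission would hide the cases most informative about whether the device can be the main means of transfer.

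Read literally, section 6.3 also leaves out the current-method patients whom the section 6.2 tests need. That is a separate defect. Repairing it by adding a second group defined by the method used would leave the present problem in place.

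**Working it through.** **Inputs from section 6.1.** 50 transfers per method; mean time 7 vs 3 minutes, SD 3.5; mean staff 5 vs 2, SD 0.5; two-sided equal-variance t-test.

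**The plan's own figure.** The standard error factor is √(1/50 + 1/50) = 0.2. For time, 4 / (3.5 × 0.2) = 5.71; for staff, 3 / (0.5 × 0.2) = 30. Power for time is above 0.9999 at the printed significance level of 0.5 and 0.9999 at 0.05. Power for staff is 1.000 at both (normal approximation). The stated power above 99% is reproduced and is not in dispute here.

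**Assumptions not in the documents.** A share f of SimPull-phase transfers is converted. A converted transfer takes T minutes in total, from T = 7 (the attempt adds no time to the manual transfer) to T = 10 (a 3-minute attempt plus 7 minutes by hand), and uses 5 staff.

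**Formulas, with conversions kept in the SimPull group.**
- Mean time = 3 + f(T − 3); time saving = 4 − f(T − 3).
- Mean staff = 2 + 3f; staff saving = 3 − 3f.
- Overstatement = (saving with conversions dropped ÷ saving with conversions kept) − 1. With conversions dropped, the savings read 4.0 minutes and 3.0 staff.
- Pooled SD of time = √{[3.5² + 3.5² + f(1 − f)(T − 3)²] / 2}.

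| f | T (min) | SimPull mean time | Time saving | Overstated by | Pooled SD | Power, two-sided 0.05 |
|---|---|---|---|---|---|---|
| 10% | 7 | 3.4 | 3.6 | 11% | 3.60 | 0.999 |
| 10% | 10 | 3.7 | 3.3 | 21% | 3.80 | 0.990 |
| 20% | 7 | 3.8 | 3.2 | 25% | 3.68 | 0.991 |
| 20% | 10 | 4.4 | 2.6 | 54% | 4.02 | 0.893 |

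For staff, the saving with conversions kept is 2.7 at 10% (3.0 / 2.7, overstated by 11%) and 2.4 at 20% (3.0 / 2.4, overstated by 25%).

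Up to 10% conversions, power for time stays at about 0.99 or higher, so the test result is little affected. The estimated saving is what moves.

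**The case against.** Several points on the other side have force.

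- **The exclusion is not an explicit rule.** A reader might infer that the plan prescribes an analysis of successes only. It does not. The phrase all-treated could cover a transfer begun with SimPull and finished by hand, and what counts as a transfer with the device is undefined. This stands as a limit on the point, but the ambiguity does not protect the analysis: classification could then be settled after the data are seen, in an unrandomised study funded by the device company (section 11.1).
- **Converted patients are not replaced under the text.** A reader might infer that the target of 50 per method lets the site enrol until 50 SimPull transfers succeed. Section 4.4.1 ties replacement to consent: "Any subject that withdraws their consent will be replaced so data is collected on 50 total subjects per transfer method". Section 5.2 likewise exceeds 50 only for withdrawals. A blocked attempt is neither.
- **The staff-availability exclusion is not a one-sided loss.** Section 4 says: "If patient consents and no IRB approved study member is available to perform the transfer, the patient will be excluded from the study". This might look like a further loss of SimPull patients, but it names no phase, acts before any transfer starts, and follows a coordinator check of availability before consent. It gives no support here.
- **A sensor block need not end in conversion.** If repositioning lets SimPull finish the move, the patient stays in the set with a longer time. So it is not established that the slowest SimPull cases disappear.
- **The cases may still be visible.** Section 4 has transfer observations entered in REDCap, and section 6.2 has every transfer timed. But no field for the method started, or for the reason for a change, is specified.
- **Using the section 5.2 groups would settle membership.** That is right, and it is the first part of the fix. Rules for timing, staff counts and reporting would still be needed.

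**Conclusion.** The point holds as a mismatch between sections 5.2 and 6.3 with a foreseeable consequence. The stated set is conditioned on actual SimPull transfer, and no rule covers blocked or converted attempts. If they are excluded, as the plain wording suggests, Endpoints 1 and 2 are biased towards SimPull.

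The size depends on a conversion rate that the protocol does not give. Under the planning means and an assumed 7 to 10 minutes and 5 staff per conversion, the time saving is overstated by 11–21% at 10% conversions and 25–54% at 20%; the staff saving is overstated by 11% and 25%. With no conversions there is no bias.

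The harm is to the effect estimate and the feasibility conclusion. The significance test is little affected at up to 10% conversions. In a 100-patient pilot this should be fixed, but it does not invalidate the design.

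**What to change.** Reword section 6.3 along these lines: all patients in either phase for whom a transfer was started, analysed under the method assigned to their phase in section 5.2, whatever method completed the transfer. Then add:

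- For the analysis, time runs from the start of the first attempt to completion by any means. The start point must be early enough that an attempt blocked before the patient moves counts as started.
- Everyone who took part is counted in the staff number.
- Converted patients are not replaced.
- REDCap records the method started, the method that completed the transfer, and the reason for any change.
- The number of conversions is reported alongside Endpoints 1 and 2.
- An analysis of completed SimPull transfers is kept as supportive.

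These are rules for analysis and recording only; they do not bear on when staff should stop an attempt. The cost is a reworded population definition, the short rules above and a small addition to the data form, with no extra patients. The one downside is a slightly less favourable SimPull mean if conversions occur. The field should be in place before the SimPull phase begins, because conversions may not be recoverable afterwards.
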